#### **Intervention Arm Only: Clinical Visit- Medical Management and Injection Visit (Ambulatory Care or ED)**

- Assessment of adverse events, medical management note.
- Repeat laboratory analysis according to XR-NTX prescribing guidelines, (urine pregnancy test if of childbearing potential; liver enzyme analysis if exhibiting signs or symptoms of liver injury). Approximately 8.5ml of blood will be drawn if applicable.
- Administer XR-NTX 380mg as an intramuscular gluteal injection.
- Those who miss appointment will be contacted though methods described in Section 4.4.2. Follow up will be performed in the ED if subject cannot be navigated to ambulatory care.

### 6.4 Visit 4: Week 8

#### **Intervention Arm Only: Clinical Visit- Medical Management and Injection Visit (Ambulatory Care or ED)**

- Assessment of adverse events, medical management note.
- Repeat laboratory analysis according to XR-NTX prescribing guidelines, (urine pregnancy test if of childbearing potential; liver enzyme analysis if exhibiting signs or symptoms of liver injury). Approximately 8.5ml of blood will be drawn if applicable.
- Administer XR-NTX 380mg as an intramuscular gluteal injection.
- Those who miss appointment will be contacted though methods described in Section 4.4.2. Follow up will be performed in the ED if subject cannot be navigated to ambulatory care.

### 6.5 Visit 5: Week 12

#### **Intervention Arm Only: Clinical Visit- Medical Management and Injection Visit (Ambulatory Care or ED) and Research Visit**

- Assessment of adverse events, medical management note.
- Repeat laboratory analysis according to XR-NTX prescribing guidelines, (urine pregnancy test if of childbearing potential; liver enzyme analysis if exhibiting signs or symptoms of liver injury). Approximately 8.5mL of blood will be drawn if applicable.
- Administer XR-NTX 380mg as an intramuscular gluteal injection.
- Those who miss appointment will be contacted though methods described in Section 4.4.2. Follow up will be performed in the ED if subject cannot be navigated to ambulatory care.

#### **Both Arms: Research Visit (ED)**

- Repeat research assessments and interview that was conducted at the initial intake/enrollment visit (see above, Week 0) plus assessment of adverse events and subject satisfaction.
- Draw 17mL of blood serum to test for biomarkers (CDT) and 8.5ml of serum for liver function tests (AST, ALT, and GGT).
- If a scheduled research visit date has passed, we will perform a research assessment at the next available opportunity (up to 6 months after the 48 week visit). Those who miss appointment will be contacted though methods described in Section 4.4.2.

CONFIDENTIAL

This material is the property of the NYU School of Medicine and Langone Medical Center. Do not disclose or use except as authorized in writing by the study sponsor

## 6.6 Visit 6: Week 16

### **Intervention Arm Only: Clinical Visit- Medical Management and Injection Visit (Ambulatory Care or ED)**

- Assessment of adverse events, medical management note.
- Repeat laboratory analysis according to XR-NTX prescribing guidelines, (urine pregnancy test if of childbearing potential; liver enzyme analysis if exhibiting signs or symptoms of liver injury). Approximately 8.5mL of blood will be drawn if applicable.
- Administer XR-NTX 380mg as an intramuscular gluteal injection.
- Those in intervention arm who miss appointment will be contacted though methods described in Section 4.4.2. Follow up will be performed in the ED if subject cannot be navigated to ambulatory care.

## 6.7 Visit 7: Week 20

### **Intervention Arm Only: Clinical Visit- Medical Management and Injection Visit (Ambulatory Care or ED)**

- Assessment of adverse events, medical management note.
- Repeat laboratory analysis according to XR-NTX prescribing guidelines, (urine pregnancy test if of childbearing potential; liver enzyme analysis if exhibiting signs or symptoms of liver injury). Approximately 8.5mL of blood will be drawn if applicable.
- Administer XR-NTX 380mg as an intramuscular gluteal injection.
- Those who miss appointment will be contacted though methods described in Section 4.4.2. Follow up will be performed in the ED if subject cannot be navigated to ambulatory care.

## 6.8 Visit 8: Week 24

### **Intervention Arm Only: Clinical Visit- Medical Management and Injection Visit (Ambulatory Care or ED)**

- Assessment of adverse events, medical management note.
- Repeat laboratory analysis according to XR-NTX prescribing guidelines, (urine pregnancy test if of childbearing potential; liver enzyme analysis if exhibiting signs or symptoms of liver injury). Approximately 8.5mL of blood will be drawn if applicable.
- Administer XR-NTX 380mg as an intramuscular gluteal injection.
- Those who miss appointment will be contacted though methods described in Section 4.4.2. Follow up will be performed in the ED if subject cannot be navigated to ambulatory care.

### **Both Arms: Research Visit (ED)**

- Repeat research assessments and interview that was conducted at the initial intake/enrollment visit (see above, Week 0) plus assessment of adverse events and subject satisfaction.
- Draw 17mL of blood serum to test for biomarkers (CDT) and 8.55ml of serum for liver function tests (AST, ALT, and GGT).
- If a scheduled research visit date has passed, we will perform a research assessment at the next available opportunity (up to 6 months after the 48 week visit). Those who miss appointment will be contacted though methods described in Section 4.4.2.

CONFIDENTIAL

This material is the property of the NYU School of Medicine and Langone Medical Center. Do not disclose or use except as authorized in writing by the study sponsor

## 6.9 Visit 9: Week 28

### **Intervention Arm Only: Clinical Visit- Medical Management and Injection Visit (Ambulatory Care or ED)**

- Assessment of adverse events, medical management note.
- Repeat laboratory analysis according to XR-NTX prescribing guidelines, (urine pregnancy test if of childbearing potential; liver enzyme analysis if exhibiting signs or symptoms of liver injury). Approximately 8.5mL of blood will be drawn if applicable.
- Administer XR-NTX 380mg as an intramuscular gluteal injection.
- Those who miss appointment will be contacted though methods described in Section 4.4.2. Follow up will be performed in the ED if subject cannot be navigated to ambulatory care.

## 6.10 Visit 10: Week 32

### **Intervention Arm Only: Clinical Visit- Medical Management and Injection Visit (Ambulatory Care or ED)**

- Assessment of adverse events, medical management note.
- Repeat laboratory analysis according to XR-NTX prescribing guidelines, (urine pregnancy test if of childbearing potential; liver enzyme analysis if exhibiting signs or symptoms of liver injury). Approximately 8.5mL of blood will be drawn if applicable.
- Administer XR-NTX 380mg as an intramuscular gluteal injection.
- Those who miss appointment will be contacted though methods described in Section 4.4.2. Follow up will be performed in the ED if subject cannot be navigated to ambulatory care.

## 6.11 Visit 11: Week 36

### **Intervention Arm Only: Clinical Visit- Medical Management and Injection Visit (Ambulatory Care or ED)**

- Assessment of adverse events, medical management note.
- Repeat laboratory analysis according to XR-NTX prescribing guidelines, (urine pregnancy test if of childbearing potential; liver enzyme analysis if exhibiting signs or symptoms of liver injury). Approximately 5mL of blood will be drawn if applicable.
- Administer XR-NTX 380mg as an intramuscular gluteal injection.
- Those who miss appointment will be contacted though methods described in Section 4.4.2. Follow up will be performed in the ED if subject cannot be navigated to ambulatory care.

## 6.12 Visit 12: Week 40

### **Intervention Arm Only: Clinical Visit- Medical Management and Injection Visit (Ambulatory Care or ED)**

- Assessment of adverse events, medical management note.
- Repeat laboratory analysis according to XR-NTX prescribing guidelines, (urine pregnancy test if of childbearing potential; liver enzyme analysis if exhibiting signs or symptoms of liver injury). Approximately 8.5mL of blood will be drawn if applicable.
- Administer XR-NTX 380mg as an intramuscular gluteal injection.
- Those who miss appointment will be contacted though methods described in Section 4.4.2. Follow up will be performed in the ED if subject cannot be navigated to ambulatory care.

CONFIDENTIAL

This material is the property of the NYU School of Medicine and Langone Medical Center. Do not disclose or use except as authorized in writing by the study sponsor

## 6.13 Visit 13: Week 44

### **Intervention Arm Only: Clinical Visit- Medical Management and Injection Visit (Ambulatory Care or ED)**

- Assessment of adverse events, medical management note.
- Repeat laboratory analysis according to XR-NTX prescribing guidelines, (urine pregnancy test if of childbearing potential; liver enzyme analysis if exhibiting signs or symptoms of liver injury). Approximately 8.5mL of blood will be drawn if applicable.
- Administer XR-NTX 380mg as an intramuscular gluteal injection.
- Those who miss appointment will be contacted though methods described in Section 4.4.2. Follow up will be performed in the ED if subject cannot be navigated to ambulatory care.

## 6.14 Visit 14: Week 48 – Study closure

### **Both Arms: Research Visit (ED)**

- Repeat research assessments and interview that was conducted at the initial intake/enrollment visit (see above, Week 0) plus assessment of adverse events and subject satisfaction.
- Draw 17mL of blood serum to test for biomarkers (CDT) and 8.5ml of serum for liver function tests (AST, ALT, and GGT).
- If a scheduled research visit date has passed, we will perform a research assessment at the next available opportunity (up to 6 months after the 48 week visit). Those who miss appointment will be contacted though methods described in Section 4.4.2.
- We will also provide subjects in both arms a referral for follow up care and substance use resources (if needed).

## 7 Statistical Plan

### 7.1 Sample Size Determination

Naltrexone has not demonstrated a robust treatment effect; however, most studies did not use the XR-preparation, are limited by poor adherence, and did not include this higher-severity population or other intervention components. We do not know what the “ideal” population for XR-NTX is, but posit that it may have a greater effect size in this more severely affected population than amongst the higher socioeconomic status population historically targeted. A recent pilot of XR-NTX suggests a possible greater effect (and acceptability) in a population similar to ours. Our literature search yielded no studies of initiating pharmacotherapy for alcohol dependence in the ED. There are only limited data on XR-NTX effects on several long-term outcomes of interest, including healthcare use, treatment engagement, and quality of life measures. ED-based case management studies demonstrate promising healthcare utilization outcomes, but most were uncontrolled and overestimated effect because of regression to the mean. The heterogeneity in study designs, interventions, and cohort characteristics precludes meta-analysis.

Determining sample size is challenged by limitations in the existing data and heterogeneity of populations. Definitively testing the relative effects of intervention components may require additional arms with as many as 75 to 200 subjects in each. Thus, we chose to start with the strongest intervention and compare it to standard care to maximize the likelihood of seeing an effect and of exploring effect size on various outcomes. The 2-arm design will minimize the loss of power and allow us to focus on the primary goal of assessing feasibility.

The first phase of study will be a feasibility and acceptability study, through which we will obtain preliminary data to inform the power analysis for the subsequent definitive trial. In the first phase, we plan to pilot the study in 50 subjects. In the second phase of study, we project enrolling 125 subjects in each of the two arms to definitively test the intervention’s effect on multiple outcomes of interest. Thus, we

CONFIDENTIAL

This material is the property of the NYU School of Medicine and Langone Medical Center. Do not disclose or use except as authorized in writing by the study sponsor

project enrolling a total of 300 subjects in both phases. These estimates are founded in the current literature and the analyses, hypotheses, and predictions of experts in the field.

[name]'s ongoing study (R01AA020836) comparing the effectiveness of oral naltrexone to XR-NTX in alcohol dependent primary care patients has a targeted enrollment of n=117 in each of the two arms to detect a 20% absolute difference in primary clinical outcomes based in the Fisher's exact test with a projected power of 90%. [name], PhDs' (R01 AA022309) four-arm RCT of alcohol dependent homeless individuals recruited from a community housing program (XR-NTX + Counseling, Placebo + Counseling, Counseling alone, Treatment as Usual) will enroll a total of 300 patients (N=75/arm). This study population is similar to the one we will be studying.

A sample of 125 subjects per arm would allow us to detect a moderate effect size (Cohen's d of slightly less than 0.40) to provide power of 0.80 or greater at  $\alpha < .05$ . Another consideration when determining sample size is to power the study to detect the reduction in ED visits that would entirely offset the cost of medication. The institutional costs of a dose of Vivitrol (XR-NTX) is comparable to the estimated institutional cost of a single ED visit to Bellevue Hospital (according to the New York State Institute Cost Review). To detect a difference of  $\geq 6$  ED visits (i.e. a 6 month course of Vivitrol) between study arms comprised of subjects having a mean of  $22 \pm 15$  ED visits per year (per our pilot study data), would require 100 subjects per arm with  $\alpha = 0.05$ ;  $\beta = 0.20$  or, more conservatively, 133 subjects per arm with  $\alpha = 0.05$  and  $\beta = 0.10$ .

**Sample Size - Performance of Biomarkers as an objective measure of Alcohol Consumption:**

Based on the literature, the correlation between the CDT level and self-reported alcohol consumption using validated, reliable methods among alcohol dependent patients ranges from approximately  $r = .35$  to  $r = .60$ . However, the relationship between CDT levels and alcohol intake may be influenced by age, gender, BMI, cirrhosis, smoking status, flushing, and other factors, such that the correlation among these subgroups groups is less (although, typically not powered to reach statistical significance). Because of potential inter-individual variation, measuring the change in CDT from an individual's baseline as a continuous variable appears to improve performance. Recent studies have also suggested that the combination of CDT and gamma-glutamyl transpeptidase (GGT), via the equation  $[0.8*\ln(GGT) + 1.3*\ln(CDT)]$ , has higher diagnostic sensitivity and stronger correlation with the actual amount of alcohol consumed than either of the parent compounds alone; in one study the correlation of CDT-GGT was  $r = .76$ ;  $p < .001$ .

We will determine the correlation between serum biomarker values and self-reported alcohol intake ascertained using the timeline followback method, which is reliable, validated, and widely used in addictions research. For our sample size calculation, the null hypothesis is there is no correlation between CDT value and reported consumption. The alternative hypothesis uses the values found in literature. The sample size calculation for each of these studies uses a type I error of 0.05. The correlation between alcohol intake and CDT level with a sample size 49, a correlation coefficient 0.39 can be detected with power 0.8. Correlation between change in CDT to change in drinking with a sample size 61, a correlation coefficient 0.35 can be detected with power 0.8. All sample size calculations are done by PASS (Power Analysis and Sample Size) 2008. See also Table 3. The first phase of study, N=50, has the approximate power required to test the primary hypotheses. We will also pool the results of Phase 1 subjects with those enrolled in phase 2.

Author	Study Results		N required
	r	p	
Mikkelsen	0.39	0.006	49
Hietala	0.59	<.001	20
Anton (all) ^	0.35	<.05	61
Anton (outliers removed) ^	0.54	0.001	24
Kim (flushers only) #	0.608	<.01	18

CONFIDENTIAL

This material is the property of the NYU School of Medicine and Langone Medical Center. Do not disclose or use except as authorized in writing by the study sponsor

Kim (non-flushers only) #	0.274	<.01	102
--------------------------------------	-------	------	-----

**Table 3:** Sample size calculation results. Ha: R0<>R1. The value “N required” shows the required sample size with power 0.8 and Type I Error 0.05. aThe correlation increased from r=.35 to r=.54 after removal of three outliers. #The Asian cohort was stratified into persons who do and do not flush upon alcohol consumption.

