### **Aim 2: Analysis of Effect:**

- a. We will explore the relative efficacy of XR-NTX+CM to standard care on decreasing acute healthcare use (ED, inpatient, other (ambulance, detoxification)) and associated expenditures.
- b. Secondarily, we will explore effects on healthcare engagement (clinic use, medication adherence, self-efficacy, motivation to change), alcohol quantity/frequency, alcohol-related consequences, quality of life measures, and cost-effectiveness.
- c. We will triangulate data sources for outcome measures to explore their correlation and to address missing data. Of specific interest, we will assess the performance of biomarkers (CDT and GGT, combinations) as an objective measure of changes in heavy drinking, which will inform the design of the second phase of study (definitive trial).

Although randomization would predict equal distribution of cofounders, we will examine their distribution and adjust accordingly. Interactions or confounding may occur between outcome domains (e.g. quality of life may have an effect on healthcare utilization); other cofounders may include age, race, sex, socioeconomic status, comorbidities, and social stability. See Figure 3.

We will ascertain healthcare utilization by triangulating data from subject self-report (Form 90) and from various other sources (pending availability), including Bellevue Hospital and New York City Health and Hospitals Corporation databases, partnering hospital medical records, EMS database of ambulance transports to all NYC EDs, and Medicaid claims data. We will report expenditures as reimbursement payments and/or using Medicaid payment rates as a cost proxy.

[figure not shown]

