**Aim 2c: Correlation of Biomarker and Self-Reported Alcohol Consumption:**

CONFIDENTIAL

This material is the property of the NYU School of Medicine and Langone Medical Center. Do not disclose or use except as authorized in writing by the study sponsor

For this substudy, data from subjects in both arms (N=50 in phase 1) will be pooled as a single cohort to assess the performance of %CDT and the %CDT-GGT combination as a marker of heavy alcohol use. We will determine the correlation between serum biomarker values and self-reported alcohol intake ascertained using the timeline follow-back (TLFB) method (within the Form 90), which is reliable, validated, and widely used in addictions research. Correlations between the measures will be assessed and inform the second phase of study.

- I. We will measure the correlation between biomarker levels and self-reported alcohol consumption using the Timeline Followback method of obtaining (a) 30-day average alcohol intake, and (b) 7-day alcohol intake. We hypothesize that biomarker levels will be correlated with alcohol intake for both periods of time.
- II. We will measure the correlation between changes in biomarker levels and changes in alcohol intake. We hypothesize that changes in alcohol intake will be correlated to the associated changes in biomarker levels.
- III. We will compare the performance of biomarkers in subjects for whom CDT has been shown to have higher diagnostic accuracy (males, low BMI, non-smoker, non-cirrhotic liver) to subjects having at least one characteristic previously found to lower the accuracy of CDT (women, high BMI, smokers, cirrhotic liver).

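### Section 7.1 says phase 1 (N=50) is approximately adequately powered, but the change correlation it sizes at N=61 has about 72% power at N=50, not 80%

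*Combined protocol and SAP*

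**What the plan says.** The biomarker sample-size part of Section 7.1 gives two calculations, both at a type I error of 0.05.

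- Level: "The correlation between alcohol intake and CDT level with a sample size 49, a correlation coefficient 0.39 can be detected with power 0.8".
- Change: "Correlation between change in CDT to change in drinking with a sample size 61, a correlation coefficient 0.35 can be detected with power 0.8".

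The adequacy statement follows shortly after: "The first phase of study, N=50, has the approximate power required to test the primary hypotheses". The next sentence adds: "We will also pool the results of Phase 1 subjects with those enrolled in phase 2". Table 3 lists six required sample sizes under a two-sided alternative. Its footnote says of the study behind the change figure: "The correlation increased from r=.35 to r=.54 after removal of three outliers".

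Section 7.2.2, Aim 2c, sets the cohort: "data from subjects in both arms (N=50 in phase 1) will be pooled as a single cohort". It lists the level correlation as hypothesis I and the change correlation as hypothesis II: "We hypothesize that changes in alcohol intake will be correlated to the associated changes in biomarker levels". Aim 2, item c, says the biomarkers will be assessed "as an objective measure of changes in heavy drinking, which will inform the design of the second phase of study (definitive trial").

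**The concern.** The adequacy sentence follows both sizings, uses the plural and makes no exception, yet 50 is 11 subjects short of the 61 just given for change: (61 − 50)/61 = 18%. The term primary hypotheses is not defined in this part of the plan, so nothing tells the reader that change is left out.

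The change result is the one that bears on phase 2, and Aim 2 intends to use it before any pooled data exist. A reader told that phase 1 is adequately powered could take a non-significant change correlation as evidence that the biomarker does not track drinking, when the sample was too small to support that reading.

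A change score also needs both a baseline and a follow-up sample. The caption of the procedures timeline in Section 3.1 expects missed research visits, but Section 7.1 makes no allowance for missing pairs.

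**Working it through.** **Inputs, all from Section 7.1 and Table 3.** Null correlation 0; two-sided α = 0.05; target power 0.80; r = 0.39 (level) and r = 0.35 (change); phase 1 N = 50.

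**Method.** Exact distribution of the sample correlation under bivariate normality, one pair per subject. The test rejects when |r| exceeds r_c = t/√(n − 2 + t²), where t is the 97.5% point of Student's t on n − 2 degrees of freedom. For n = 50, t = 2.011 and r_c = 2.011/√(48 + 4.043) = 0.279. Power is the probability that |r| exceeds r_c at the assumed true correlation.

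**Step 1: reproduce the plan's figures.** The smallest n with power of at least 0.80:

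| r | Table 3 | Exact method |
|---|---|---|
| 0.39 | 49 | 49 |
| 0.59 | 20 | 20 |
| 0.35 | 61 | 61 |
| 0.54 | 24 | 24 |
| 0.608 | 18 | 18 |
| 0.274 | 102 | 102 |

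All six agree. As a cross-check for r = 0.35, the Fisher z formula gives n = ((1.960 + 0.842)/atanh 0.35)² + 3 = (2.802/0.3654)² + 3 = 61.8, which rounds up to 62, one more than the exact method.

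**Step 2: power at N = 50.**

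| Correlation | N | Exact power |
|---|---|---|
| Level, r = 0.39 | 50 | 0.814 |
| Change, r = 0.35 | 61 | 0.801 |
| Change, r = 0.35 | 50 | 0.716 |
| Change, r = 0.54 (outliers removed) | 50 | 0.987 |

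Fisher z check for change at N = 50: √47 × 0.3654 = 2.505; 2.505 − 1.960 = 0.545; Φ(0.545) = 0.707. Simulation with 200,000 runs per cell gave 0.717 for change and 0.815 for level at N = 50.

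The chance of a non-significant result at r = 0.35 is therefore 1 − 0.716 = 28%, against the 20% accepted at N = 61. The smallest correlation with 80% power at N = 50 is 0.384.

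**Step 3: missing pairs (assumed, since the documents give no follow-up rate).** At r = 0.35:

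| Assumed loss | Pairs | Exact power |
|---|---|---|
| 10% | 45 | 0.668 |
| 20% | 40 | 0.614 |
| 30% | 35 | 0.554 |

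**Step 4: precision.** If r = 0.35 is observed in 50 pairs, the 95% interval is tanh(0.3654 ± 1.96/√47) = tanh(0.0796) to tanh(0.6513) = 0.08 to 0.57.

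**Step 5: pooled data.** At r = 0.35, power is above 0.999 with 300 pairs and 0.993 with an assumed 150.

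**The case against.** The strongest reply is that the sentence refers only to the level correlation. The null hypothesis stated for the sizing concerns CDT value and consumption. Hypothesis I has two parts, for 30-day and 7-day intake, which would by itself explain the plural. On that reading 50 against 49 is right. The reading is possible, but the documents never state it, and the sentence follows both sizings without singling one out. If level alone is meant, the text should say so.

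Other points on that side carry weight:

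- The sentence says approximate, and the figures 61 and 50 appear close together, so nothing is hidden. But 81% against 80% is approximate in a way that 72% at best is not.
- r = 0.35 is the less favourable of the two change values in Table 3, and N = 50 meets four of the six rows. However, 0.35 is the value the text itself chose for sizing change.
- Pooling cures the final analysis. It does not cure a statement about phase 1, and Section 15.1 says funding for phase 2 is still to be sought.
- Three follow-up samples per subject (Section 6), late research visits (Section 3.1) and missing-data sensitivity analyses (Aim 2c) may limit the loss of pairs. They do not raise the number of independent subjects above 50.
- The analysis is secondary and exploratory (Sections 2 and 3.3), and no phase 2 decision is tied to a p-value. This stands, and it is why the point is minor.

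**Conclusion.** The concern holds and is minor. On the plan's own inputs, phase 1 has the stated power for the level correlation (about 81%) but not for the change correlation at r = 0.35: about 72% with 50 complete pairs, some 8 points below target, and lower with any missing pairs. The result assumes the two-sided test shown in Table 3, bivariate normality, a Pearson correlation and one pair per subject. A one-sided test would give about 81% at N = 50, but it contradicts Table 3. The error lies in the adequacy sentence, not in the sample sizes, and its consequence is confined to how the phase 1 change result is interpreted.

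**What to change.** Replace the adequacy sentence in Section 7.1 with wording such as:

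> Phase 1 (N=50) provides about 81% power for the level correlation (r=0.39). For the change correlation at r=0.35 it provides about 72% power with 50 complete baseline and follow-up pairs, and less with missing pairs; the smallest correlation detectable with 80% power at 50 pairs is about 0.38. Phase 1 change correlations will be reported with 95% confidence intervals, and the analysis will be repeated in the pooled phase 1 and phase 2 data as planned.

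This drops the undefined term and is correct whichever hypotheses it was meant to cover. Keep the phase 1 analysis in Aim 2c; do not move the test solely to the pooled data, which would make it depend on phase 2 being funded. Do not write an assumed follow-up rate into the protocol.

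The cost is small: one sentence becomes three, the stated phase 1 power for change is less favourable, and confidence intervals are added to the change correlations. Subjects, samples and visits are unchanged.
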